**Definite:**

A clinical event, including laboratory test abnormality (if applicable), for which there is no uncertainty in the relationship to test product administration (e.g., positive recalling).

## **11.4 Adverse Event Reporting**

All observed or volunteered adverse events occurring during the study period, at any time from the signature of the informed consent until the final study evaluation, regardless of treatment group or suspected causal relationship to study drug, will be recorded on the adverse event page(s) of the eCRF.

The need to capture this information is **not dependent** upon whether the adverse event is considered to be related to the use of the study drug. Also, adverse events resulting from concurrent illnesses and reactions to concurrent medications must be reported. In order to avoid vague, ambiguous, or colloquial expressions, the AE will be recorded using standard medical terminology rather than the patient's own words.

Each AE should be described in detail in the eCRF: nature of the event (a sign, a symptom or a diagnosis preferably), onset and stop dates, severity, relationship to study drug, seriousness (see below *Section 11.5*), action taken including corrective therapy and outcome.

AEs that are believed to be at least possibly related to study drug should be followed until satisfactory resolution or acceptable stabilization.

For all AEs, the Investigator must pursue and obtain the necessary information both to determine the outcome of the adverse event and to assess whether it meets one of the criteria for classification as a serious adverse event requiring immediate notification to the **PV Department of ICTA PM** (see *Section 11.5*). For all AEs, sufficient information should be obtained by the Investigator to determine the causality of the adverse event (e.g., study drug or other illness).

## **11.5 Serious Adverse Events**

### **11.5.1 Definition**

A **Serious Adverse Event (SAE)** is any untoward medical occurrence that at any dose:

1. Results in death;
2. Is life-threatening;
3. Results in patient's hospitalization or prolongation of existing hospitalization;
4. Results in a persistent or significant disability/incapacity; or
5. Results in congenital anomaly/birth defect
6. Is a medically significant event

A **Suspected Unexpected Serious Adverse Reaction (SUSAR)** is a suspected adverse event considered as related to the study drug and which is both unexpected and serious.

Important medical events that may not result in death, be life-threatening, or require hospitalization may be considered as serious adverse events when, based upon appropriate medical judgment, they may jeopardize the patient or may require medical or surgical intervention to prevent one of the outcomes listed above. Examples of such medical events include allergic bronchospasm requiring intensive treatment in an emergency room or at home, blood dyscrasias or convulsions that do not result in patient hospitalization, or the development of drug dependency or drug abuse.

A life-threatening adverse event is any adverse event that places the patient at immediate risk of death from the reaction as it occurred (e.g., it does not include a reaction that, had it occurred in a more severe form, might have caused death).

Initial hospitalization is defined as any inpatient admission (even if less than 24 hours). For chronic or long-term in patients, inpatient admission also includes transfer within the hospital to an acute/intensive care inpatient unit (e.g., from the psychiatric wing to a medical floor, from a medical floor to the coronary care unit, from the neurological floor to the tuberculosis unit).

Inpatient admission in the absence of a precipitating, treatment-emergent, clinical adverse event may meet criteria for “seriousness”, is not considered as an adverse event and thus is not subject to immediate reporting. For example:

1. Admission for treatment of a pre-existing condition not associated with the development of a new adverse event or with a worsening of the pre-existing condition (e.g., for work-up of persistent pre-treatment lab abnormality)
2. Social admission (e.g., patient has no place to sleep)
3. Administrative admission (e.g., for yearly physical exam)
4. Protocol-specified admission during a clinical trial (e.g., for a procedure required by the study protocol)

5. Optional admission not associated with a precipitating clinical adverse event (e.g., for elective cosmetic surgery).

The following events are neither considered as inpatient admission nor serious adverse events:

1. Emergency Room/Accident and Emergency/Casualty Department visits
2. Outpatient/same-day/ambulatory procedures
3. Observation/short-stay units
4. Rehabilitation facilities
5. Hospice facilities
6. Respite care (e.g., caregiver relief)
7. Skilled nursing facilities
8. Nursing homes

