A second Phase II study called CHI-SQUARE, in patients with Acute Coronary Syndrome has also been completed. It was an ascending dose, placebo-controlled, double-blind, dose-response study that enrolled 507 patients (3:1 ratio active:placebo). The full study report is still in preparation; however, preliminary results indicate that CER-001 did not meet its primary endpoint of a reduction in total atheroma volume (TAV) as measured by IVUS for the 12 mg/kg CER-001 treated patients compared to the placebo patients. Methodological concerns regarding the IVUS analysis, as detected in the EXPRESS study, also pertain to CHI-SQUARE. An independent and blinded analysis of the IVUS images was conducted by a different IVUS core lab (SAHMRI, Adelaide Australia). In this post-hoc but blinded reanalysis, the 3 mg/kg treatment group showed consistent improvement relative to baseline and was numerically superior to placebo in all analysis populations. In the Modified Per Protocol analysis, statistical significance of 3 mg/kg over placebo was achieved for some of the IVUS measurements (7).

[figure not shown]

Figure 1. Change in IVUS parameters by treatment group and analysis population  
(LS Means from ANCOVA modeling with nonparametric testing due to non-normality of data; mITT = modified intent-to-treat, mPP = modified per-protocol population; PPP = per protocol population)

In general, CER-001 and placebo had a similar safety profile. The incidence and type of SAEs were similar for CER-001 and placebo, with the possible exception of infusion reactions (drug hypersensitivity reactions, anaphylaxis, and adverse drug reactions).

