## 5 RISK BENEFIT STATEMENT

All patients enrolled in this study will have four 3T-MRI measurements during a time period of 48 weeks. 3T-MRI is a non-invasive imaging technique that does not involve exposure to ionizing radiation. The magnetic field itself is not harmful; however, imbedded metallic fragments such as shrapnel or implanted medical devices that contain metal such as pacemakers may malfunction or cause problems during an MRI exam.

Patients in this study will have two FDG-PET scans during the study, the first one will be performed at baseline and the second and last assessment will be done at week 24. FDG-PET is routinely used in clinical practice. The total radiation exposure in the study corresponding to the two FDG-PET CT scans is 9.4 milli-Sievert. Labelled glucose, F-deoxyglucose, has no known side effects. No adverse effects are expected.

Two thirds of the patients randomized in the trial will receive twenty-nine infusions of CER-001 (8mg/kg) and one third will receive twenty-nine infusion of placebo. More than 400 patients have been exposed to CER-001 in previous clinical trials including 122 patients exposed to 12 mg/kg CER-001 in phase II study. Overall CER-001 has been well tolerated. The incidence and type of SAEs were similar for CER-001 and placebo, with the possible exception of infusion reactions which occurred more frequently with CER-001 and may occur more frequently at higher doses. These reactions were reversible in all cases and either resolved spontaneously or after management with antihistamines, steroids and/or IV fluids. A phase II study (CARAT) aiming to enroll 292 patients for evaluating the potential benefit of CER-001 in ACS patients is currently ongoing.

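### Protocol section 11.5.1 conflicts with itself on seriousness: its closing list excludes emergency-room and short-stay care from serious adverse events without a qualifier, while its own example allows such an event to be serious.

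*Protocol*

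**What the plan says.** Protocol section 11.5.1 defines an SAE by six criteria. Hospitalisation is one. Being life-threatening is another, and the sixth reads "Is a medically significant event". The section then says that important medical events which do not lead to death, threat to life or hospitalisation "may be considered as serious adverse events when, based upon appropriate medical judgment" supports it. It illustrates this as follows: "Examples of such medical events include allergic bronchospasm requiring intensive treatment in an emergency room or at home".

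After paragraphs on what counts as an admission, and on which admissions are not adverse events at all, the section ends with eight items introduced by: "The following events are neither considered as inpatient admission nor serious adverse events". The first is "Emergency Room/Accident and Emergency/Casualty Department visits" and the third is "Observation/short-stay units". Same-day and ambulatory procedures are the second. The rest are rehabilitation, hospice, respite and nursing settings. Nothing says that the other seriousness criteria still apply.

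The seriousness flag is used in two places that matter here. Protocol section 11.5.2 requires an SAE to be reported within 24 hours of first awareness. SAP section 7.5.1 counts patients with a serious TEAE.

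**The concern.** The definition makes seriousness depend on the event, and the closing list makes it depend on where the patient was treated. Take a patient with a severe allergic reaction after an infusion who is treated in an emergency room, or kept for a few hours in a short-stay unit, and goes home. The criteria and the example let the investigator call this serious. The closing list, taken at its word, says it is not.

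The conflict bears on the main safety signal that the protocol itself names for CER-001. Section 3.3.2 singles out "infusion reactions (drug hypersensitivity reactions, anaphylaxis, and adverse drug reactions") as the possible exception to a similar SAE profile in the acute coronary syndrome trial. Section 5 repeats the point across the programme: SAE incidence and type were similar to placebo "with the possible exception of infusion reactions which occurred more frequently with CER-001". Section 11.6 anticipates allergic responses, with wheezing among the symptoms. The protocol's example of a serious event without admission is therefore close to the reaction that is expected. Safety and tolerability over 24 weeks is one of the two primary objectives, so consistent seriousness coding across sites is worth having.

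**Working it through.** No plan figure is in dispute. The check sets the texts side by side.

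1. **What the criteria cover.** Under 11.5.1 an event is serious if any one of the six criteria is met. Two of them, threat to life and medical significance, do not depend on admission.

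2. **What the example adds.** The bronchospasm example names both an event and a setting, and the setting is an emergency room. It is permissive: such events may be considered serious on medical judgment. It shows that emergency-room care is compatible with seriousness, not that every such event is serious.

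3. **What the list removes.** Had the introductory line stopped at inpatient admission, it would only have narrowed the hospitalisation criterion, and no conflict would arise. The added words on serious adverse events reach the other criteria too. The preceding list, of admissions that are not adverse events, is limited to admissions with no precipitating adverse event. The closing list carries no such limit.

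4. **Whether another section resolves it.** Section 11.4 requires every AE to be assessed against the SAE criteria and its seriousness to be recorded, without exemption by setting. This favours judging the event itself. But it sends the reader to section 11.5, where the conflict sits.

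5. **What a literal reading would lose.** The 24-hour report (11.5.2), the serious-TEAE row (SAP 7.5.1) and the individual SAE listing (SAP 7.5).

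6. **What would remain.** The event is still recorded as an AE (11.4) and tabulated by system organ class and preferred term. If it qualifies, it also appears in the SAP rows for severe TEAEs, related TEAEs, or TEAEs leading to dose reduction or discontinuation. Events leading to those dose actions are listed individually.

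7. **Size, if it happened.** 30 patients randomised 2:1 gives 30 × 2/3 = 20 on CER-001 and 30 × 1/3 = 10 on placebo.
   - Planned double-blind CER-001 infusions: 20 × 29 = 580. Up to 12 open-label infusions follow for each patient who continues.
   - One CER-001 patient reclassified from serious to non-serious: 1/20 = 5 percentage points.
   - One placebo patient reclassified: 1/10 = 10 percentage points.

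   The documents give no rate of infusion reactions and do not say where they are treated. These figures show sensitivity to a single patient and predict nothing.

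**The case against.** The strongest reply is that the list names places of care, not medical events. A nursing home or an emergency-room visit is not an untoward medical occurrence, so the list can only mean that such a visit or stay does not in itself make an event serious. It follows directly on paragraphs about admissions, and section 11.4 requires every AE to be judged on the criteria. The bronchospasm example names the event and the setting together and is arguably the more specific text. There is also some practice on record: section 3.3.2 reports that in the open-label homozygous FH study an urticarial reaction that resolved rapidly with treatment was classed as a treatment-related SAE.

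Much of this stands. The harmonious reading is available and well supported, and a reader should not infer that the list overrides the example because it is more specific. The earlier study is weaker evidence, since its SAE wording is not in these documents.

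Three further inferences are tempting and not supported:

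- **That such reactions are usually treated in an emergency room or short-stay unit.** Section 5 says that they resolved spontaneously or with antihistamines, steroids or IV fluids, and names no setting. Treatment in the infusion clinic is not expressly on the list.
- **That the reactions would disappear from the safety record.** They would remain as AEs and could appear in several other SAP rows, and the DSMB reviews unblinded safety data (SAP section 9).
- **That SUSARs would be lost.** A SUSAR must be unexpected against the Investigator's Brochure, which is not available here, and section 11.6 already anticipates allergic responses.

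What the reply does not remove is the unqualified sentence. The sound reading has to be worked out from other paragraphs, and staff at about 15 sites may not all work it out the same way.

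**Conclusion.** The inconsistency within section 11.5.1 is real and should be fixed. It is a wording fault in a reporting rule; the efficacy analyses are untouched. A literal reading would class a reaction treated in an emergency room, same-day or short-stay setting as non-serious, and so remove it from the 24-hour report and the serious-TEAE count, but not from the AE record.

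A reader might go further and conclude that serious infusion reactions will be under-reported, or that the serious-event comparison is biased towards CER-001. The documents do not support either as fact. No missed event is shown. A bias towards CER-001 would need three things: sites apply the list literally, reactions that would otherwise be serious are treated in the listed settings, and the higher frequency with CER-001 described in section 5 recurs. Under those assumptions each CER-001 patient affected moves that arm's serious-event rate by 5 percentage points. A placebo patient affected would move the other arm by 10, so the direction does not follow from the wording alone.

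**What to change.** Reconcile the parts of section 11.5.1. Limit the closing list to its evident purpose, for example: *The following do not by themselves count as inpatient admission. The event that led to them must still be assessed against all the other seriousness criteria and reported within 24 hours if any of them is met.* Put the same sentence on the SAE report form.

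Send sites a short memo. Before database lock, have a blinded pharmacovigilance review check the seriousness coding of recorded AEs that involved emergency or short-stay care, so that events entered under the present wording are coded on the same basis.

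The cost is a one-sentence amendment, a memo and a limited blinded check of existing records. The downside is possibly a few more SAE reports.

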### **11.5.2 Reporting**

Any SAE, occurring during the study period, at any time from the signature of the informed consent until the final study evaluation, regardless of treatment group or suspected causal relationship to study drug, must be reported by the investigator **within 24 hours** from the date of the first awareness to:

**the PV Department of ICTA PM**  
**by email to [[contact]](mailto:[contact]) (or by [contact])**

The Investigator (principal investigator or any other investigator designed by the principal investigator as authorized to notify safety issues) will be requested to complete and sign a separate SAE report form in addition to the information recorded on the adverse event page of the eCRF. All available information concerning the SAE (copies of laboratory results, other exams, hospitalization reports, autopsy report and other appropriate documents) will be transmitted anonymously with the SAE report form.

Any laboratory result abnormality fulfilling the criteria for a SAE should be reported as such, in addition to being recorded as an AE in the eCRF. As soon as the diagnostic term for the laboratory result abnormality is available, the SAE report should be updated to include the diagnosis as event term, if possible.

In case of SUSAR, the Sponsor or its representative will be responsible for their notification to the relevant regulatory authorities as outlined in the ICH Guidelines. All investigators participating in studies of CER-001 will also be informed as required by regulations.

### **11.5.3 Follow-up of Serious Adverse Events**

For any new information relating to an already notified SAE, the investigator will have to complete a SAE Follow-up report which will be transmitted by fax/email, **within 24 hours**, to the **PV Department of ICTA PM to [[contact]](mailto:[contact]) (or by fax: [name])**

accompanied with anonymized copies of the applicable laboratory results, other exams and/or the hospitalization reports.

The reporting of the follow-up information will be done in the same manner as initial SAE reports. Any SAE, regardless of the causal relationship to the study drug, must be followed until satisfactory resolution or stabilization (in case of sequelae) of the event. This can sometimes mean that the follow-up continues after the patient study termination. Satisfactory resolution may include referral to the patients usual care provider.

#### **11.5.4 Serious Adverse Events occurring after the study**

All SAEs occurring at any time after the end of the study, likely to be related to the study drug or to a study procedure, according to the investigator, must be notified according to the process for SAE reporting described above.

#### **11.6 Expected Adverse Drug Reactions**

CER 001 has previously been administered to humans in single doses ranging from 0.25 to 45 mg/kg. No treatment related AE were reported in that single dose study. In the completed multiple dose studies the adverse event profile has been consistent with what would be expected from the experience of Phase I and Phase II studies and from treating these populations of patients.

AEs that would be reasonable to expect based on repeat dosing in animal toxicity studies include increased liver enzymes, and changes to red blood cell indices although these have not been observed with single or multiple human doses at a rate higher than that observed with placebo. Other AEs that may be anticipated are local injection site reactions and allergic responses. These reactions may include one or more of the following symptoms: wheezing, eye itching, eye swelling, facial swelling, rash, feeling cold, decrease in body temperature, cold sweat, cold shivers, chest pressure, chest pain, jaw pain, decreased blood pressure, increased blood pressure, fatigue, dizziness, headache, nausea, vomiting, stomach pains, and diarrhea.

#### **11.7 Liver and kidney expected adverse reactions which may lead to drug withdrawal**

To date, there have been no significant laboratory abnormalities associated with the use of CER-001 in humans, however toxicology studies in mice and monkeys indicate that liver and kidney are possible target organs for toxicity.

Specific requirements for hepatic and renal abnormalities are detailed below.

**Hepatic Stopping Criteria:**

In the case of Liver Function Test elevation  $> 3 \times \text{ULN}$ , additional workup may be required within 24 hours of the event by the investigator in close consultation with the Sponsor according to established protocols. This is to rule out possible cases of Hy's law.

Patients should have dosing withheld if the most recently obtained serum ALT or AST exceeds five times the upper limit of normal. If the most recently obtained serum ALT or AST elevation is greater than the upper limit of normal but less than five times the upper limit of normal, the patients may receive their next dose, which may be reduced in consultation with the Sponsor (see *Section 10.3* for more details).

**Discontinuation criteria:**

Any of the following findings should prompt discontinuation from study drug:

- First observation of ALT or AST  $> 8 \times \text{ULN}$
- ALT or AST  $> 5 \times \text{ULN}$  for more than 2 weeks
- Any case of Hy's Law (i.e., ALT or AST  $> 3 \times \text{ULN}$  and TBL  $> 2 \times \text{ULN}$  or jaundice)

All Hy's Law cases (i.e., ALT or AST  $> 3 \times \text{ULN}$  and TBL  $> 2 \times \text{ULN}$  or jaundice) have to be reported as adverse events.

Re-challenge following discontinuation of study drug for either aminotransferase elevations or for potential or confirmed Hy's Law cases must not be attempted under any circumstances, unless a decision about re-challenge has been endorsed by the Sponsor.

**Renal Stopping Criteria:**

Special attention will be paid to:

1. Unexplained serum creatinine values greater than:
  - a. two times the upper limit of the normal range at two consecutive test points following dosing; or
  - b. one and one half (1.5) times the upper limit of the normal range at three consecutive test points following dosing or
2. Creatinine Clearance  $\leq 30 \text{ mL/min}$ .

Creatinine clearance will be measured from serum creatinine based on the Cockcroft-Gault formula:

$$\text{CrCl} = \frac{[140 - \text{age (years)}] \times \text{weight (kg)}}{[72 \times \text{serum creatinine (mg/dL)}]} \times 0.85 \text{ for female patient}$$

If the study drug is thought to have caused the abnormalities, the Investigator may elect to discontinue study drug dosing. The cause should be thoroughly documented in the patient record. Such renal impairments should be reported as adverse events.

## **11.8 Pregnancy**

If a patient becomes pregnant during the treatment period of the study or within 15 weeks after the last dose of study drug, the pregnancy must be reported.

If the pregnancy occurs during the treatment period, the study drug should be discontinued.

Pregnancy itself is not an AE; however pregnancies must always be followed until completion or until pregnancy termination (i.e. induced abortion) and the outcome must be notified to the Sponsor or its representative.

The Investigator will be provided with a Pregnancy Report Form. This form must be completed and sent to the **PV Department of ICTA within 24 hours of awareness**. If the outcome of the pregnancy meets the criteria for a SAE (i.e. spontaneous miscarriage, congenital anomaly) the investigator must follow the procedures for SAEs reporting. Any complications occurring during pregnancy will be recorded as AEs and/or SAEs.

If the partner of a male patient becomes pregnant during the treatment period of the study or within the 15 weeks following the last dose of study drug, this should be reported to the investigator.

A specific informed consent will be provided to allow the collection of data concerning the follow-up and outcome of the pregnancy of the patient's partner.

Reporting and follow-up of the partner pregnancy will be done as mentioned above.

